## 11 GENERAL DEFINITIONS AND DERIVATIONS

### 11.1 Phases, periods, visits

Assessments that are summarized in the report are those defined in the study protocol and recorded at the corresponding visits in the eCRF.

#### 11.1.1 Analysis visits

To allow analysis of data at the relevant planned (scheduled) visits, all recorded assessments, including unscheduled ones, are assigned to the most appropriate analysis visit according to the best fitting time-window for that visit [see [Table 11](#)]. The visit windows are based on the number of days from first study treatment intake. In the majority of cases it is expected that the analysis visit is the same as the scheduled visit.

**Analysis Relative Day** is estimated for several assessments (e.g., vital signs, laboratory data, physical examination). It refers to the number of days elapsed since first study treatment intake date plus 1 (e.g., Day 1 is the day of first study treatment intake). For dates prior to first study treatment intake, study day is the negative number of days elapsed between the date under consideration and the day of first study treatment intake. Therefore, the study day is never 0.

**Analysis Relative Day to EOT** is estimated for several assessments (e.g., vital signs, laboratory data, physical examination). It refers to the number of days elapsed since last study treatment intake date (e.g., Analysis Relative Day to EOT is null when the date of assessment and the date of last study treatment intake are equal).

**Analysis Window Difference from Target** is defined as the absolute difference between **Analysis Relative Day** and **Analysis Window Target**. It is necessary to adjust for the fact that there is no day 0 in the event that Analysis Relative Day and Analysis Window Target are not of the same sign.

**Table 11 Study phases, period and analysis visits**

| Period | Phase           | Analysis Visit (N) | Analysis Visit | Analysis Window Beginning Time point (Days) | Analysis Window Ending Time point (Days) | Analysis Window Valid Relative Range (Days) | Analysis Window Target (Days) |
|--------|-----------------|--------------------|----------------|---|--|---|-------------------------------|
|        | Screening phase | 1                  | Screening      | Lowest                                      | -1                                       | -30; -1                                     | .                             |
| 1      | Treatment phase | 2                  | Day 1          | 1   | 1  | 1; 1  | 1                             |
| 1      | Treatment phase | 3                  | Week 2         | 2   | 21                                       | 2; 21                                       | 15                            |
| 1      | Treatment phase | 4                  | Week 4         | 22  | 42                                       | 22; 42                                      | 29                            |
| 1      | Treatment phase | 5                  | Week 8         | 43  | 70                                       | 43; 70                                      | 57                            |
| 1      | Treatment phase | 6                  | Week 12        | 71  | 105                                      | 71; 105                                     | 85                            |
|        | Follow-up phase | 7                  | EOS*           | 106   | 196                                      | 106; 196                                    | 127                           |

\*for EOS, it is either Analysis Relative Day > 105 or Analysis Relative Day to EOT > 42.

*Please note for that subjects who were not randomized, all assessments must be assigned to Analysis Visit 1 (Screening).*

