### 5.1.9 Premature discontinuation of study treatment

The decision to prematurely discontinue study treatment may be made by the subject, the investigator, or Actelion. The main reason and whether discontinuation of study treatment is the decision of the subject, the investigator, or Actelion must be documented in the eCRF.

A subject has the right to prematurely discontinue study treatment at any time by withdrawal from study treatment only or by withdrawal from any further participation in the study (i.e., premature withdrawal from the study [see Section 9.2]).

The investigator should discontinue study treatment for a given subject if, on balance, she/he believes that continued administration would be contrary to the best interests of the subject. Study treatment may be discontinued in response to an AE, lack of efficacy (including disease progression, treatment failure, worsening of subject condition), a protocol deviation (including not meeting eligibility criteria, non-compliance with study requirements, such as non-compliance with study treatment intake or visit attendance), or if the subject is lost to follow-up. Study-specific criteria for discontinuation of study treatment are described in Section 5.1.10.

Premature discontinuation of study treatment may also result from a decision by Actelion, e.g., in case of premature termination or suspension of the study [see Section 9.3]. A subject who prematurely discontinues study treatment is not considered as withdrawn from the study, provided that the subject's consent for this limited participation in the study has not been withdrawn. Subjects who prematurely discontinue study treatment will be asked to return for an EOT visit within 7 days of last study treatment intake, to attend an EOS Visit 6 weeks after the last dose of study treatment and will be followed-up for a total of 16 weeks after last study treatment intake (telephone call follow-up for pregnancy and SAEs).

A subject who prematurely discontinues study treatment and withdraws consent to participate in any further study assessments is considered as withdrawn from the study. Subjects who die or are lost to follow-up are also considered as withdrawn from the study. Withdrawal from the study and follow-up medical care of subjects withdrawn from the study is described in Sections 9.2 and 9.4, respectively.

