### **8.3 Follow-up period**

#### **8.3.1 Visit 7 – EOS**

The EOS visit will take place 6 weeks ( $\pm$  5 days) after last study treatment dose. The visit includes:

- Recording of changes in concomitant medications and background SLE therapies since Visit 6
- Recording of methods of contraception (for WOCBP)
- Abbreviated physical examination
- SLEDAI-2K and PGA
- SBP/DBP
- 12-lead ECG
- Spirometry (under the responsibility of the pulmonary function laboratory technician or expert)
- Ophthalmological examination (under the responsibility of the ophthalmologist)
- Hematology (including coagulation tests) and blood chemistry
- Serum pregnancy test (for WOCBP)
- ANA, anti-dsDNA antibodies, complement C3 and C4
- Exploratory biomarkers
- Lymphocyte subsets
- Urinalysis
- PK sampling
- Recording of AEs/SAEs

A urine pregnancy test will be dispensed to WOCBP.

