### 11.2.3 Full Analysis Set

The Full Analysis Set (FAS) includes all randomized subjects. In order to adhere to the intention-to-treat principle as much as possible:

- Subjects will be evaluated according to the dose they have been randomized to (which may be different to the dose they have received)
- Unless otherwise stated, all available efficacy data up to the EOS date will be included, irrespective of whether a subject has stopped study treatment earlier or has received any SLE treatment other than that to which the subject was randomized to.

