### 5.5.1 Main pharmacodynamic variable

The main variable is the change in lymphocyte count in peripheral blood from baseline to EOT, defined as:

- Total lymphocyte count at EOT – total lymphocyte count at baseline

The value at baseline is defined as the last non-missing value obtained from a sample taken prior to the first study treatment intake.

The value at EOT is defined last post-baseline value from a sample taken at least 21 days after the first study treatment intake (with no interruptions) and no later than 7 days after the last study treatment intake for the analyses on the PDS and on the PPS.

The value at EOT is defined as the last post-baseline value up to Week 12 for the analyses on the FAS (application of the intention-to-treat principle [ITT] utilizing the Last observation carried forward [LOCF] technique for missing data).

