### 5.6 Pharmacokinetic variables

PK samples are collected at Visit 3 (Week 2), Visit 4 (Week 4), Visit 5 (Week 8), Visit 6 (Week 12/ EOT), and Visit 7 (EOS).

PK variables comprise

- $C_{trough}$  ACT-334441 plasma concentrations prior to dosing at Weeks 2, 4, 8, and 12 (EOT);
- ACT-334441 plasma concentration at EOS (i.e., 6 weeks after study treatment discontinuation).

The following PK endpoint is defined:

- Cenerimod (ACT-334441) plasma concentrations at each analysis visit.

For analysis visits Weeks 2, 4, 8, samples must be taken 1 calendar day after the previous dose and before the next dose (see Section 11 for details of how this is handled).

For analysis visit Week 12, samples must be taken within 1 to 7 calendar days after the last dose (see Section 11 for details of how this is handled).

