### **10.11 Analysis of pharmacokinetic variables**

For PK variables [defined in Section 5.6], quantitative descriptive statistics (including geometric mean and 95% CI) for ACT-334441 plasma concentrations are presented by visit and treatment group for the PKS. It includes only data from samples that are taken according to the protocol i.e.,

- For Week 2, 4 and 8: trough samples, i.e., samples taken before dosing and one day after the previous dose
- For Week 12: samples taken within 1 to 7 days following the last dose.

The evolution of the values over time is provided in graphical format (one figure: one boxplot per treatment group and analysis visit, from baseline to EOS).

A listing of individual data is produced on the SCR.

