### **Additional expressions**

#### **End of treatment (EOT)**

For analyses ran on the FAS or the SAF, an additional observation (AVISITN = 6.1, AVISIT = 'End-of-treatment', DTTYPE = 'LOCF') is created for all subjects with at least one post-baseline assessment available. It is populated with the latest non-missing value assigned from analysis visit Week 2 to analysis visit Week 12 according to the LOCF principle.

In addition, for analyses ran on the PDS or the PPS, an extra observation (AVISITN = 6.2, AVISIT = 'End-of-treatment', DTTYPE = 'LOCF') is created for all subjects with at least one non-missing post-baseline assessment performed at least 21 days after the first study treatment intake but no later than 7 days after the last study treatment intake. It is populated with the latest value available fitting these criteria.

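### SAP Table 11 labels End-of-Study visits 37 to 42 days after last intake as Week 4, 8 or 12 in early discontinuers, while visits on days 43 to 47 are labelled EOS

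*SAP*

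**What the plan says.** Protocol 8.3.1 states "The EOS visit will take place 6 weeks" after the last dose, with a window of ± 5 days. Protocol 5.1.9 applies the same timing to subjects who stop early: they are asked "to attend an EOS Visit 6 weeks after the last dose of study treatment". The visit is therefore tied to last intake, whenever that was.

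SAP 11.1.1 assigns every recorded assessment to an analysis visit by a day window counted from first intake. The windows in Table 11 are Week 2, Days 2–21; Week 4, Days 22–42; Week 8, Days 43–70; Week 12, Days 71–105; and EOS, Days 106–196. A footnote adds a second route: "for EOS, it is either Analysis Relative Day > 105 or Analysis Relative Day to EOT > 42". The same section sets the count relative to EOT at zero on the date of last intake.

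The labels then feed the End-of-treatment record used for the FAS and the Safety Analysis Set (AVISITN 6.1): "It is populated with the latest non-missing value assigned from analysis visit Week 2 to analysis visit Week 12 according to the LOCF principle". SAP 5.5.1 defines that value by time, not by label: "The value at EOT is defined as the last post-baseline value up to Week 12 for the analyses on the FAS". SAP 10.6.2 adds that the FAS carry-forward has no time limit. Protocol 11.2.3 takes FAS data "irrespective of whether a subject has stopped study treatment earlier". The PDS and PPS use a separate record (AVISITN 6.2), limited to samples within 7 days of last intake.

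**The concern.** The footnote should catch the EOS visit of a subject who stopped early, because that visit can fall well before Day 106. It requires more than 42 days since last intake, but the protocol window opens at day 37 and is centred on day 42. The first six of its eleven days, including the target day, fall outside the rule. No other rule in the SAP restores the scheduled label.

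Three kinds of output are at stake:

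- EOS summaries lose these values. Examples are lymphocyte subsets (SAP 5.7.3.2) and lymphocyte reversibility (Protocol 11.4.3.5.2).
- By-visit tables, including the Week 12 complete-case look in SAP 10.6.2, gain values taken about six weeks off drug.
- The FAS End-of-treatment record treats two visits inside the same protocol window differently according to a one-day difference in date.

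**Working it through.** **Inputs.** EOS visit k = 37 to 47 days after last intake (Protocol 8.3.1). Day windows and footnote from SAP Table 11. Last intake on study day L, with Day 1 as first intake, so the visit falls on study day L + k. Completers have last intake at about Day 84.

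**The plan's own figure.** Table 11 gives an EOS target of Day 127. The Week 12 target is Day 85, and 85 + 42 = 127. The target reproduces, and it fits a completer.

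**Rule as written.** The label is EOS if L + k > 105 or k > 42; otherwise it follows the day window.

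| k | Week 4 | Week 8 | Week 12 | EOS |
|---|---|---|---|---|
| 37 | L = 1–5 | L = 6–33 | L = 34–68 | L ≥ 69 |
| 42 (target day) | none | L = 1–28 | L = 29–63 | L ≥ 64 |
| 43 to 47 | none | none | none | all L |

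Example: last intake on Day 56. A visit 42 days later is on Day 98 and is labelled Week 12. One day later, on Day 99, it is labelled EOS.

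**Extent.** For L = 1–63, all six days 37–42 are mislabelled. For L = 64–68 the number of mislabelled days is 5, 4, 3, 2 and 1. From L = 69 it is zero. Over L = 1–84 there are 84 × 11 = 924 combinations, of which 63 × 6 + (5 + 4 + 3 + 2 + 1) = 378 + 15 = 393 are mislabelled: 210 as Week 12, 168 as Week 8 and 15 as Week 4. The grid is unweighted. It counts dates and gives no probability.

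**FAS record.** In-window EOS visits dated by Day 105 number 393 (days 37–42) plus 62 + 61 + 60 + 59 + 58 = 300 (days 43–47), so 693 in all. The record takes the 393 (57%) and leaves out the 300 (43%).

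**By-visit tables.** SAP 11.1.2 keeps the value closest to target within a window. For L ≤ 63 the EOT visit (days 1–7 after last intake) never shares a window with the mislabelled EOS visit, so the EOS value stands unless an unscheduled assessment falls there. For L = 64–68 they share the Week 12 window in 35 of 105 combinations. The EOT value is closer to target in all 35 and is kept.

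**Candidate cut-offs.** >= 42 leaves 393 − 63 = 330 mislabelled; >= 37 leaves none. Checked for L = 79–89 and 0–47 days after last intake, >= 37 changes 0 of 528 completer labels. An EOT visit, due by day 7, cannot be caught by it.

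**Size in one arm (illustration).** Assume a baseline of 2.0 × 10⁹/L and a 64% reduction that still holds at the EOT visit, so a count of 0.72 and a change of 1.28. Suppose one subject of 12 has the EOS visit on day 42 instead of day 43, so that the EOS value replaces the EOT value in the FAS record. If the count has recovered to 1.0, the arm mean moves by (1.0 − 0.72)/12 = 0.023, or 1.8% of 1.28. With full recovery it moves by 1.28/12 = 0.107, or 8.3%.

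**The case against.** The strongest reply is that the FAS is meant to include off-drug data. That stands. A reader might infer that the values from days 37–42 wrongly dilute the FAS effect, but Protocol 11.2.3 and SAP 5.5.1 and 10.6.2 admit them. Measured against those definitions, the departure is the omission of days 43–47. It follows that changing the footnote alone would also remove days 37–42 and take the FAS further from its stated policy. The policy does not, however, explain a split between day 42 and day 43, and neither would an on-treatment policy. The treatment-emergent period of six weeks inclusive may be where the cut came from, but it governs safety attribution, not visit names.

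A reader might also infer that a six-week PK sample is certainly lost. SAP 5.6 defines the endpoint as "ACT-334441 plasma concentration at EOS (i.e., 6 weeks after study treatment discontinuation") and reports by analysis visit. A sample relabelled Week 12 would fail the condition in SAP 10.11, "For Week 12: samples taken within 1 to 7 days following the last dose", and one relabelled Week 8 would fail the trough condition there. But SAP 10.11 speaks mostly of visits, and SAP 11.2.20 uses scheduled visit numbers and counts days from the last dose. Whether Table 11 applies to PK samples is unclear, so the loss is possible but not shown.

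Nor can the footnote be blamed for off-drug ECG or blood-pressure values in the worst-value record from discharge to Week 12. SAP 11.1.1 can be read there by date, in which case days 43–47 enter as well.

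Finally, the cases may be few. Only last intake by Day 68 matters, the Week 4 label needs last intake on Days 1–5, and the outputs touched are supportive, exploratory or descriptive. All of that stands.

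**Conclusion.** The mismatch is real and follows from the documents' own day counts: more than 42 days in Table 11 against 42 ± 5 days in the protocol. It misplaces EOS visits on days 37–42 for last intake by Day 63, and some of days 37–41 for last intake on Days 64–68. EOS summaries and by-visit tables are affected, and the FAS End-of-treatment record does not follow its own definition.

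Severity is minor. The main analysis on the PDS and the PPS End-of-treatment record are protected by the 7-day limit, and completers are labelled correctly. The documents do not give the number of early discontinuers; with none there is no effect. The shift of about 2%, and at most 8.3%, in one arm's FAS mean rests on the assumed counts above and on one affected subject in an arm of 12. It measures the effect of the day-42/43 split, not bias in the treatment effect.

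**What to change.** Make two changes together.

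1. Change the Table 11 footnote so that an assessment is EOS if Analysis Relative Day > 105 or Analysis Relative Day to EOT >= 37. Every in-window EOS visit then carries the EOS label.
2. Derive the FAS End-of-treatment record (AVISITN 6.1) from all post-baseline values dated up to Day 105, whatever their visit label. This matches SAP 5.5.1 and 10.6.2 and treats days 37–47 alike.

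The cost is one footnote, one sentence and one extra derivation; no new data are needed. The downside is that some further off-drug values, from days 43–47, enter the supportive FAS analyses. The footnote settles the label only: if a subject has several values in the EOS window, SAP 11.1.2 still selects by distance from Day 127, which suits completers better than early discontinuers. It would also help to state whether PK samples are assigned through Table 11 or by scheduled visit.

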### **Additional expressions**

#### **End of treatment (EOT)**

For analyses ran on the FAS or the SAF, an additional observation (AVISITN = 6.1, AVISIT = 'End-of-treatment', DTTYPE = 'LOCF') is created for all subjects with at least one post-baseline assessment available. It is populated with the latest non-missing value assigned from analysis visit Week 2 to analysis visit Week 12 according to the LOCF principle.

In addition, for analyses ran on the PDS or the PPS, an extra observation (AVISITN = 6.2, AVISIT = 'End-of-treatment', DTTYPE = 'LOCF') is created for all subjects with at least one non-missing post-baseline assessment performed at least 21 days after the first study treatment intake but no later than 7 days after the last study treatment intake. It is populated with the latest value available fitting these criteria.

### On Day 1 (post-dose)

For 12 lead ECG and blood pressure measurements, an additional observation (AVISITN = 2.5, AVISIT = ‘During day 1’, DTTYPE = ‘MINIMUM’ and/or DTTYPE = ‘MAXIMUM’) is created for all subjects with at least one post-baseline assessment performed on Day 1, after first study treatment intake, and is populated according to the worst observation carried forward (WOCF) principle.

### From discharge on day 1 through EOT

For 12 lead ECG and blood pressure measurements, an additional observation (AVISITN = 7.1, AVISIT = ‘From Week 2 through Week 12’, DTTYPE = ‘MINIMUM’ or/and DTTYPE = ‘MAXIMUM’) is created for all subjects with at least one post-baseline assessment performed after discharge on Day 1 and up to Week 12 and is populated according to the WOCF principle.

### During Study Period

For 12 lead ECG and blood pressure measurements, an additional observation (AVISITN = 7.2, AVISIT = ‘During study period’, DTTYPE = ‘MINIMUM’ and/or DTTYPE = ‘MAXIMUM’) is created for all subjects with at least one post-baseline assessment performed from Day 1, after first study treatment intake, up to EOS and is populated according to the WOCF principle.

#### 11.1.2 Retests and multiple assessments in the same visit window

Unless specified otherwise, for findings (e.g., 12 lead ECG, laboratory data), in the case of multiple results in the same analysis visit/ time point, the results included in summary tables are selected according to the following rules:

- Prior to first study drug administration

For the same parameter and the same subject, only the latest non-missing result available prior to first study drug administration is retained for analysis.

- After first study drug administration

For the same parameter and the same subject in the same visit window, only the result of the first non-missing assessment (closer to the target day) is retained for analysis. In case of equidistant values from the planned time point, the last assessment is considered for the analyses. Where multiple assessments fall on the same day, then the latest is used.

The records to be taken into account in the analysis are to be flagged (the variable **Analysis Record Flag** is defined to support the selection of the right assessment). All results are listed.

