## 6.2 Safety endpoints

Treatment-emergent period is defined as the time from first study treatment intake up to 6 weeks (inclusive) after last study treatment intake.

- Treatment-emergent AEs, SAEs, and AESIs#;
- AEs leading to premature discontinuation of study treatment;
- Changes in 12-lead ECG variables (HR, PR, QRS, QT, QT corrected for heart rate on the basis of Bazett's formula [QTcB] and QT corrected for heart rate on the basis of Fridericia's formula [QTcF]), from pre-dose to selected post-dose assessments (1 h, 2 h, 3 h, 4 h, 5 h, 6 h) on Day 1 and on day of study drug re-initiation;
- Occurrence of treatment-emergent 12-lead ECG outliers (e.g., HR, PR, QTc defined in the Statistical Analysis Plan [SAP]);
- Occurrence of treatment-emergent 12-lead ECG abnormalities;
- Occurrence of treatment-emergent ECG-Holter abnormalities on Day 1;
- Change in SBP and DBP from baseline up to EOS;
- Change in FEV1 and FVC, expressed in absolute value (L) and percent value from baseline up to EOS;
- Occurrence of treatment-emergent decrease of FEV1 or FVC > 15% from baseline values;
- Change in laboratory parameters (hematology, blood chemistry, and urinalysis) from baseline up to EOS;
- Treatment-emergent laboratory abnormalities according to CTCAE 2010 v4.03 [CTCAE 2010] and FDA guidelines [FDA 2009] (for ALT/AST/TBL);
- Change in protein-to-creatinine ratio from baseline to EOT;
- Change in body weight from baseline to EOT.

#AESI considered for the analyses are described in [Appendix 3](#).

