## 8.5 Additional visits for re-initiation of study treatment

Subjects may need to be monitored at the study site when re-initiating study drug following a study drug treatment interruption. Re-initiation visits should be conducted for study treatment interruptions which started prior to Day 14 [see Section 5.1.8].

Note that a subject can be re-initiated only once during the study duration

The same post-dosing procedure as described in Section 8.2.1.2 (Visit 2 – Day 1 – Randomization and post-dose assessment) must be followed:

- Hourly 12-lead ECG and SBP/DBP assessments for 6 hours or until the patient meets the discharge criteria (under the responsibility of the CSA [see Appendix 4]). If discharge criteria are not met after 12 hours, the subject should be permanently discontinued.
- Recording of AEs and SAEs (please refer to Sections 7.2.2, 7.2.4 and 10.1.5 for reporting of AEs with onset on Day 1).
- Recording of changes in concomitant medications and background SLE therapies since previous visit.
- Study drug accountability for compliance review.

These visits for post-dose monitoring of the subjects when re-initiating study treatment are additional unscheduled visits. The regular scheduled study visits must be resumed according to the original visit and assessment schedule. If the visit occurs at the same time as a regular visit, all assessments of the regular visit have to be performed in addition.

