### **11.4.3.2 Cardiac safety**

#### *11.4.3.2.1 12-lead ECG assessments*

Descriptive summary statistics by visit and study treatment will be provided for observed treatment-emergent values and absolute changes from pre-dose in numeric 12-lead ECG values (HR, PR, QRS, QT, QTcB, QTcF). Data will be summarized from pre-dose to each post-dose assessments on Day 1 and also at the re-initiation of study drug.

Notable abnormalities for selected 12-lead ECG parameters (HR, PR, QT, QTcF) will be summarized for all data on Day 1, Week 12 and also at the re-initiation of study drug.

In addition treatment-emergent morphological ECG abnormalities will be summarized descriptively (using data from the ECG provider).

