## 5.8.7 Electrocardiogram

### 5.8.7.1 12-lead ECG variables and findings

#### - 12-lead ECG variables

The 12-lead ECG measurements and qualitative ECG findings (e.g. rhythm, ectopy, conduction and morphology) are provided by the ECG central reader, along with the overall interpretation of the ECG (Normal/ Abnormal).

The following endpoints are defined:

- Absolute values and change from baseline to each post-baseline assessment up to EOS (i.e., each post-dose time point on Day 1 and each post-dose analysis visit up to EOS) for each parameter;
- Occurrence of treatment-emergent 12-lead ECG notable abnormalities;
- Occurrence of treatment-emergent 12-lead ECG qualitative abnormalities (medical review findings).

For the following ECG parameters, the occurrence of treatment emergent notable abnormalities is assessed according to the criteria defined in the table below.

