### **10.9.3 Electrocardiography (ECG)**

#### ***10.9.3.1 12-lead ECG variables and findings***

The following displays of ECGs are provided:

- Quantitative descriptive statistics for absolute values of ECG parameters by treatment group and analysis visit and time point.
- Quantitative descriptive statistics for the absolute change from baseline to 1h, 2h, 3h, 4h, 5h and 6 h post-dose on Day 1 and each post-baseline analysis visit by treatment group and parameter.
- Boxplots of absolute values at baseline and all post-baseline analysis visits and time points: one figure per parameter and per treatment group. Notable abnormality thresholds are displayed on the plots as an overlay.
- Notable ECG abnormalities for QTcB, QTcF, HR, PR and QRS are summarized by treatment group by presenting the number and percentage of subjects with any abnormality at each post-baseline analysis visit and time point, at any time on Day 1 (from 1 hour post-dose to discharge), at any time after Day 1 (from discharge on Day 1 up to EOT), and at any time post-baseline (from 1 hour post-dose to EOS), 95% Clopper-Pearson confidence intervals are presented for the proportions.
- The number and percentage of subjects with any treatment-emergent ECG qualitative abnormalities at any time (ECG findings) by category and reported term are summarized by treatment group.

The denominator for percentages is the number of subjects with at least one post-baseline assessment in the considered interval.

All ECG data (parameters and findings) are listed by treatment group, subject and visit. All post-treatment notable abnormalities are flagged and qualitative abnormalities (as transferred by the ECG central reader) are listed.

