#### 10.9.5 Vital signs and body weight

For body weight, a summary table presenting the value at baseline, value at Visit 6 (EOT) and the change from baseline is produced by treatment group.

Standing SBP and DBP (mmHg) are not included in the summary tables but included in the listings.

For supine SBP and DBP (mmHg), the following displays are provided:

- Quantitative descriptive statistics for absolute values by treatment group and analysis visit and time point.
- Quantitative descriptive statistics for the absolute change from baseline to 1h, 2h, 3h, 4h, 5h and 6 h post-dose on Day 1 and each post-baseline analysis visit by treatment group and parameter. This table is repeated for the measurements taken on day of study drug re-initiation, if applicable.
- Boxplots of absolute values at baseline and all post-baseline analysis visits and time points: one figure per parameter and per treatment group. Notable abnormality thresholds are displayed on the plots as an overlay.
- Notable BP abnormalities are summarized by treatment group by presenting the number and percentage of subjects with any abnormality at each post-baseline analysis visit and time point, at any time on Day 1 (from 1 hour post-dose to discharge), at any time after Day 1 (from discharge on Day 1 up to EOT), and at any time post-baseline (from 1 hour post-dose to EOS), 95% Clopper-Pearson confidence intervals are presented for the proportions.

The denominator for percentages is the number of subjects with at least one post-baseline assessment in the considered interval.

All data (values and changes) are listed by treatment group, subject and visit. All marked abnormalities are flagged.

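### The SAP omits, without declaring it, the protocol's 12-lead ECG summaries for the day of re-initiation, and its windowing rule can let a post-dose re-initiation ECG stand as the pre-dose Week 2 value

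*SAP*

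**What the plan says.** **Protocol.** Section 6.2, repeated in 11.3.3, defines ECG change from pre-dose to the 1-6 h readings "on Day 1 and on day of study drug re-initiation". Section 11.4.3.2.1 carries this into the analysis: "Data will be summarized from pre-dose to each post-dose assessments on Day 1 and also at the re-initiation of study drug". The same section plans a summary of notable ECG abnormalities on Day 1, at Week 12 and at re-initiation.

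**SAP, ECG.** Section 5.8.7.1 limits the endpoint to "each post-dose time point on Day 1 and each post-dose analysis visit up to EOS". Section 10.9.3.1 plans: "Quantitative descriptive statistics for the absolute change from baseline to 1h, 2h, 3h, 4h, 5h and 6 h post-dose on Day 1", together with the post-baseline analysis visits. The notable-abnormality intervals are Day 1, after Day 1 and any time post-baseline. None is specific to re-initiation.

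**SAP, blood pressure.** Section 10.9.5 does plan for re-initiation, after its hourly change table: "This table is repeated for the measurements taken on day of study drug re-initiation, if applicable".

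**Visit assignment.** Protocol 8.5 says of re-initiation: "These visits for post-dose monitoring of the subjects when re-initiating study treatment are additional unscheduled visits". SAP 11.1.1 says that "all recorded assessments, including unscheduled ones, are assigned to the most appropriate analysis visit". SAP Table 11 has no re-initiation visit. Within a window, SAP 11.1.2 keeps the result nearest the target day, then the later one if two are equidistant, and finally: "Where multiple assessments fall on the same day, then the latest is used".

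**The concern.** Re-initiation repeats the Day 1 cardiac monitoring, and the protocol asks for its ECG results to be summarized separately. Followed as written, the SAP produces no such summary for ECG, although it does for blood pressure. That pattern looks more like an oversight than a decision. SAP Section 4, which lists changes and clarifications to the protocol's analyses, is silent on it, and the protocol synopsis reproduced in SAP 15.1 still lists the endpoint.

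The second issue is where those ECGs go. Outside Day 1 and re-initiation, protocol Table 1 (footnote 5) specifies pre-dose ECGs only. If an hourly post-dose reading from a re-initiation day is selected as the Week 2 value, the Week 2 heart rate, PR and abnormality results mix two kinds of measurement, in dose groups planned at 12 subjects.

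**Working it through.** **1. Planned ECG analyses, side by side.**

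| Item | Protocol | SAP |
|---|---|---|
| ECG change to 1-6 h, Day 1 | 6.2, 11.3.3, 11.4.3.2.1 | 5.8.7.1, 10.9.3.1 |
| ECG change to 1-6 h, re-initiation day | 6.2, 11.3.3, 11.4.3.2.1 | absent |
| Notable ECG abnormalities, re-initiation day | 11.4.3.2.1 | absent as a separate summary |
| Blood pressure change, re-initiation day | not named as a separate summary | 10.9.5 |
| Declared as a change in SAP Section 4 | not applicable | no |

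The data exist: protocol 7.2.2 and Table 1 require pre-dose and hourly post-dose ECGs at re-initiation. The reference value is missing. SAP 11.2.1 sets baseline as the last value before the first dose of double-blind treatment, and SAP 11.2.11 uses that baseline for ECG. No SAP variable therefore measures change from the re-initiation day's own pre-dose ECG.

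**2. When re-initiation can occur.** Inputs: the interruption starts between Day 1 and Day 14, and re-initiation takes place within 7 days of the first missed dose (protocol 5.1.8.1). Assumption: Day 1 is always dosed on site, so the first missed dose is Day 2 at the earliest.
- Earliest re-initiation: 2 + 1 = Day 3.
- Latest re-initiation: 14 + 7 = Day 21.
- Week 2 window in SAP Table 11: Days 2-21, target Day 15.

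Every possible re-initiation day lies inside the Week 2 window.

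**3. When a re-initiation ECG is selected.** Let V be the scheduled Week 2 visit day, 15 ± 3 = Days 12-18 (7 values), and R the re-initiation day, Days 3-21 (19 values). That gives 7 × 19 = 133 pairs. Read per visit window, SAP 11.1.2 selects the re-initiation day if |R − 15| < |V − 15|, or if the two distances are equal and R > V. If R = V, it selects the latest reading of that day, taken 6 h or more after dosing.

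| V | Same day | R closer to Day 15 | Equidistant, R later | Total |
|---|---|---|---|---|
| 12 | 1 | 5 | 1 | 7 |
| 13 | 1 | 3 | 1 | 5 |
| 14 | 1 | 1 | 1 | 3 |
| 15 | 1 | 0 | 0 | 1 |
| 16 | 1 | 1 | 0 | 2 |
| 17 | 1 | 3 | 0 | 4 |
| 18 | 1 | 5 | 0 | 6 |
| Sum | 7 | 18 | 3 | 28 |

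Displacement occurs in 28/133 = 21% of pairs; the scheduled value is kept in 105/133 = 79%. Counting each combination of missed-dose day and re-initiation day separately gives (118 + 43 + 15)/637 = 176/637 = 28%. Both are counts of calendar possibilities, not expected patient frequencies. If the scheduled Week 2 ECG is missing, the re-initiation reading is taken for any R in the window, unless another eligible ECG is nearer Day 15.

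**4. Weight of one such value.** With 12 subjects in a dose group, one displaced value is 1/12 = 8% of that Week 2 cell.

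**The case against.** The case on the other side is substantial, and much of it stands.

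- *A reader might infer that re-initiation ECGs go unanalysed.* They do not. They are listed, and they enter the after-Day-1 and any-time abnormality summaries, the qualitative findings table and the worst-value records (SAP 5.8.7.1, 10.9.3.1, 11.1.1). What is missing is the dedicated re-initiation summary.
- *A reader might infer that the hourly readings always become the Week 2 value.* Nearness to Day 15 is applied first. With Visit 3 on Day 15 exactly, displacement needs re-initiation on Day 15 as well. The lead-in of SAP 11.1.2 and SAP 10.9 both speak of visit or time point. Read that way, hourly readings would not compete with a pre-dose record. However, the operative bullet of 11.1.2 refers to the visit window, so the text supports two readings that give different tables.
- *A reader might infer that an acute effect is being reported as steady state.* The SAP does not call Week 2 steady state, and protocol 1.3.2.1 places steady state at 20-32 days.
- *A reader might infer a known size of heart-rate effect.* The maximum at about 4 h and resolution within 12 h come from the single-dose part of the Phase 1 study. For the multiple-dose range, protocol 1.3.2.3 describes the changes as not clinically significant. No effect at re-initiation is given.
- *A reader might want these readings removed from the after-Day-1 interval.* That would be unsound. SAP 5.8.7.1 defines the interval as running from Day 1 discharge to EOT, and SAP 10.9 counts all safety data up to EOS.

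The titles under SAP Section 13 (list of tables) are not visible in the available text, so a table shell there cannot be excluded. It would still lack a matching endpoint definition.

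**Conclusion.** The omission is a plain inconsistency: a protocol safety endpoint and a planned abnormality summary have no counterpart in the SAP's ECG sections, and the change is not declared. This does not depend on any windowing assumption.

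The windowing point is real but conditional. It needs a re-initiated subject, a per-window reading of SAP 11.1.2, and either one of the 28 in 133 day arrangements or a missing scheduled ECG. The number of re-initiations is not given, each subject can have only one (protocol 5.1.8.1), and the number affected may be small or zero. Blood pressure is less exposed, because after Day 1 the SAP takes the averaged record (11.2.17.1), whereas hourly post-dose pressures are single readings (protocol 7.2.4). The ECG derivation has no such filter.

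The consequence is confined to descriptive safety reporting. No hypothesis test and no lymphocyte result is affected. The SAP should be amended because it loses a protocol endpoint that is cheap to restore. Taking the re-initiation day's own pre-dose ECG as the reference is the natural reading of protocol 6.2 and 11.4.3.2.1, although neither states which day's pre-dose applies.

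**What to change.** 1. In SAP 5.8.7.1 and 10.9.3.1 add, if applicable, a re-initiation-day table of ECG values at 1-6 h and changes from that day's pre-dose ECG, plus the notable-abnormality summary for that day. Define the reference explicitly. Copying the blood pressure sentence is not enough, because that table measures change from study baseline, which SAP 11.2.17.1 takes from the Day 1 pre-dose readings.
2. In SAP 11.1.2 state that post-dose ECGs from a re-initiation visit are not eligible as the Week 2 analysis-visit value. Under that rule, none of the 133 day pairs puts a post-dose re-initiation reading in the Week 2 cell.
3. Keep these readings in the after-Day-1 and any-time-post-baseline worst-value and abnormality summaries.

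The cost is one extra table shell and a wording change. No new data are needed, and if nobody was re-initiated the table is marked not applicable.
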